11.5.3.2 Statistical methods for pharmacokinetic analyses

Descriptive statistics of pharmacokinetic parameters will include mean, SD, and CV, min and max. When a geometric mean will be presented it will be stated as such. Since Tmax is generally evaluated by a nonparametric method, median values and ranges will be given for this parameter.

At day 1 and Day 28, AUC and Cmax will be summarized for each cohort along with 90% two-sided confidence intervals computed on the log-scale and back-transformed. All subjects with available PK parameters and no protocol deviation excluding them from the PK analysis set will be part of this computation.

[figure not shown]
If 3 or more cohorts are included in part 1 of the study, then dose-proportionality will be explored for PK parameters (AUCtau and Cmax) by fitting a power model (PK parameter = α dose $^{\beta}$). A natural logarithmic transformation will be applied for the power model, which implies to a general linear model to the log transformed PK parameter with a fixed continuous log-dose effect. The model becomes $\log(\text{PK parameter}) = \log(\alpha) + \beta \log(\text{Dose}) + \varepsilon$. The estimate of the common slope β , which is the exponent in the power model, and the 90% confidence interval of the exponent will be obtained. Dose proportionality will be considered if the 90% confidence interval for β is completely contained within the pre-specified critical region (bL, bU).

LJN452 plasma concentration data will be listed by treatment, subject, and visit/sampling time point. Descriptive summary statistics will be provided by treatment and visit/sampling time point. Additionally summary statistics may also be provided for the LJN452 plasma concentration data with a breakdown by UDCA stratum as appropriate.

Summary statistics will include mean (arithmetic and geometric), SD, CV (arithmetic and geometric), median, minimum and maximum. An exception to this is Tmax where median, minimum and maximum will be presented. Concentrations below LLOQ will be treated as zero in summary statistics and for PK parameter calculations. A geometric mean will not be reported if the dataset includes zero values. Pharmacokinetic parameters will be calculated as described in [Section 8.5](#) and will be listed by treatment and subject.

11.5.4 Pharmacokinetic / pharmacodynamic interactions

The relationship between PK and key primary and/or secondary PD parameters will be explored.

11.6 Sample size calculation

A recently published study of a compound with similar mechanism ([Mason et al 2010b](#); [Hirschfield et al 2015](#)) on a similar population (study of INT-474 in combination with UDCA in patients with PBC) suggests that the treatment difference over placebo at Day 28 is approximately -50% with a standard deviation ~ 0.28. In Part 1, with 12 patients per cohort randomized to LJN452 or placebo with a randomization ratio of 2:1, there is approximately 85% probability that the upper limit of a 90% two-sided confidence interval of treatment difference between LJN452 versus placebo will exclude 0, if the underlying treatment difference is about -50% in terms of percent change from baseline. A total of up to 5 cohorts of LJN452 at different dose levels may be studied. Assuming a dropout rate of approximately 20%, 15 patients per cohort will be enrolled in Part 1, with a total of at least 30 (up to 75) patients.

Part 2 of the study will be conducted on patients currently taking UDCA and UDCA naïve patients. A published study ([Jones et al 2011](#)) (study of INT-474 as monotherapy in patients with PBC) suggests that the effect size of change from baseline in GGT is bigger in naïve patients than in the non-responder population studied in Part 1. So, we can assume a treatment effect of at least 50% as well as a standard deviation of 0.28. Based on power calculation for Part 1, enrolling at least 30 patients to receive an LJN452 dose and 20 patients to receive the placebo treatment in Part 2 will provide at least 95% power that a two-sided significance test at nominal level 5% will detect a difference (same analysis as in Part 1). A total of 80 patients are planned to be randomized to LJN452 or placebo with a 3:3:2 ratio (Dose Level 1:Dose Level 2:Placebo). Assuming a dropout rate of approximately 10%, 88 patients will be enrolled in Part 2.

11.7 Power for analysis of key secondary variables

Data from 30 patients receiving each LJN452 dose and 20 patients receiving placebo in Part 2 will provide 81% power to detect a 15% treatment difference in change from baseline ALP between an LJN452 dose and placebo, based on a 2-sided t-test at the 0.05 significance level assuming a standard deviation of 17.8%, obtained from the interim analysis of the first 2 cohorts in Part 1.

11.8 Interim analyses

Planned interim analyses will take place in Parts 1 and 2 of the study.

Planned interim analyses will be performed in Part 1; a) when at least 12 patients in Cohort 1 have completed 4 weeks of dosing and have finished the day 28 post dose assessments; b) when the same time point is reached for at least 12 subjects in each cohort of Part 1.

The purpose of the first interim analysis is to assess patient safety, to evaluate the assumption on intra-subject variability of GGT which was used for sample size calculations, and to select a dose for the next cohort. An ANCOVA model will be fitted to estimate the change from baseline in GGT to day 28 and its variability, and an unblinded sample size re-estimation conducted. The results may be used to adjust the size of the next cohort.

In the subsequent interim analyses in Part 1, placebo data from all cohorts will be pooled in the ANCOVA model to evaluate the treatment difference between each dose level of LJN452 versus placebo. The model described in the primary analysis section will be fitted, as it is indeed the same analysis which will be included in the final study report.

Unblinded interim analysis results from Part 1 will be reviewed by an internal Novartis Interim Analysis Team which may include some CTT members. The Interim Analysis Team may communicate interim results to relevant Novartis teams for information, consulting and/or decision purposes. The composition of the interim analysis team will be decided before the FPFV and a roster of membership maintained in the trial master file.

The Interim Analysis Team may communicate interim results (e.g., evaluation of PoC criteria or information needed for planning/modifying another study) to relevant Novartis teams for information, consulting and/or decision purposes.

No further dissemination of interim results based on un-locked data should occur, in particular not with individuals involved in treating the study's subjects or assessing clinical data (e.g., ECGs, images, symptoms) obtained in the study.

In Part 2 of the study an interim analysis is planned when approximately 40 patients have completed their Week 8 visit. The purpose of this interim analysis is to review the sample size (calculated based on GGT and ALP changes) to assess if it is also adequate to provide precise enough treatment difference estimates in itch parameters, a key tolerability endpoint. A blinded sample size re-estimation will be performed and a proposal to increase the sample size submitted to the DMC as needed. The DMC will decide whether it is appropriate to increase the sample based on an unblinded interim analysis, which will be performed by a study independent statistician and programmer with outputs provided to the DMC only. Recruitment will continue while the IA is being performed.

11.9 Interim analyses on locked data

This study will utilize a staggered lock of the clinical database, so that the data can be locked after completion of Part 1, or a set of Cohorts in Part 1.

Once a Cohort's data has been locked, treatment codes for the relevant cohort(s) will be released and made available for data analysis.

The results from the locked interim analysis can be communicated beyond Novartis to groups including, but not limited to individuals treating the study's subjects, Health Authorities and on clinical registries.

12 Ethical considerations

12.1 Regulatory and ethical compliance

This clinical study was designed and shall be implemented and reported in accordance with the ICH Harmonized Tripartite Guidelines for Good Clinical Practice, with applicable local regulations (including European Directive 2001/20/EC, US Code of Federal Regulations Title 21, and Japanese Ministry of Health, Labor, and Welfare), and with the ethical principles laid down in the Declaration of Helsinki.

12.2 Responsibilities of the investigator and IRB/IEC

Before initiating a trial, the investigator/institution should obtain approval/favorable opinion from the Institutional Review Board/Independent Ethics Committee (IRB/IEC) for the trial protocol, written informed consent form, consent form updates, subject recruitment procedures (e.g., advertisements) and any other written information to be provided to subjects. Prior to study start, the investigator is required to sign a protocol signature page confirming his/her agreement to conduct the study in accordance with these documents and all of the instructions and procedures found in this protocol and to give access to all relevant data and records to Novartis monitors, auditors, Novartis Quality Assurance representatives, designated agents of Novartis, IRBs/IECs, and regulatory authorities as required. If an inspection of the clinical site is requested by a regulatory authority, the investigator must inform Novartis immediately that this request has been made.

For multi-center trials, a Coordinating Investigator will be selected by Novartis around the time of Last Patient Last Visit to be a reviewer and signatory for the clinical study report.

12.3 Publication of study protocol and results

Novartis assures that the key design elements of this protocol will be posted in a publicly accessible database such as clinicaltrials.gov. In addition, upon study completion and finalization of the study report the results of this trial will be either submitted for publication and/or posted in a publicly accessible database of clinical trial results.

13 Protocol adherence

This protocol defines the study objectives, the study procedures and the data to be collected on study participants. Additional assessments required to ensure safety of subjects should be administered as deemed necessary on a case by case basis. Under no circumstances should an investigator collect additional data or conduct any additional procedures for any research related purpose involving any investigational drugs.

Investigators must apply due diligence to avoid protocol deviations. If the investigator feels a protocol deviation would improve the conduct of the study this must be considered a protocol amendment, and unless such an amendment is agreed upon by Novartis and approved by the IRB/IEC/REB it cannot be implemented. All significant protocol deviations will be recorded and reported in the CSR.

ALT or AST > 3 x ULN and INR > 1.5	
 • Discontinue study drug • Hospitalize, if clinically appropriate • Establish causality and complete liver event checklist (in SOM) 	--	Continue monitoring with Repeat tests ^a until resolution ^c	--	--
ALT or AST > 8 x ULN	
 • Discontinue study drug • Hospitalize if clinically appropriate • Establish causality and complete liver event checklist (in SOM) 	--	Continue monitoring with Repeat tests ^a until resolution ^c	--	--
ALT or AST > 2 X Baseline AND > 3 x ULN AND accompanied by symptoms^b	
 • Discontinue study drug • Hospitalize if clinically appropriate • Establish causality and complete liver event checklist (in SOM) 	--	Continue monitoring Repeat tests ^a until resolution ^c	--	--

Criteria	First Action	Result	Second Action	Result	Third Action
ALT or AST > 2 X Baseline AND > 5 to \leq 8 x ULN	
 Repeat tests^a within 48 hours of notification of result HOLD study drug until repeat test results available Establish causality and complete liver event checklist (in SOM) 	↑	Part 1 
 Discontinue study drug 		
 Continue monitoring with Repeat tests^a 2-3 times per week until resolution ^c Update liver event checklist
			Part 2 
 Reduce dose (Table 6-1). Restart study drug at reduced dose Repeat tests^a 2-3 times a week after re-starting study drug Update liver event checklist (in SOM) 	↑	Part 2 If elevated after re-starting study drug, discontinue study drug 
 Continue monitoring with Repeat tests^a until resolution ^c Update liver event checklist
				↓	If values normalize, continue with reduced dose. 
 Repeat tests^a two and three weeks after re-starting study drug If levels remain \geq 2x Baseline 3 weeks after dose reduction, discontinue study drug 
 Continue monitoring with Repeat tests^a until resolution ^c Update liver event checklist

Criteria	First Action	Result	Second Action	Result	Third Action
		↓	Part 1 
 Restart study drug at assigned dose level Repeat tests^a 2-3 times a week after re-starting study drug Update liver event checklist Part 2 
 Maintain assigned dose level Restart study drug at assigned dose level Repeat tests^a 2-3 times a week after re-starting study drug Update liver event checklist 	↑	Both Parts If elevated after re-starting study drug, discontinue study drug
				↓	Both Parts 
 Continue study drug at assigned dose level
ALT or AST > 2 X Baseline AND ≤ 5 × ULN (patient is asymptomatic)	
 Repeat tests^a within 48 hours of notification of result 	↑	Part 1 
 Discontinue study drug Part 2 
 Repeat tests^a visit within 48 hours HOLD study drug until repeat test results available Complete liver event checklist 		Part 1 
 Continue monitoring with Repeat tests^a 2-3 times per week until resolution ^c Update liver event checklist Part 2 
A. Reduce dose (Table 6-1).
 
 Restart study drug at reduced dose Repeat tests^a 2-3 times a week after re-starting study drug 
B. If elevated after re-starting study drug, discontinue study drug
 
 Continue monitoring with Repeat tests^a until resolution ^c Update liver event checklist

Criteria	First Action	Result	Second Action	Result	Third Action
				↓	Part 2 
• Maintain assigned dose level
		↓	Both Parts 
• Maintain assigned dose level		
Alkaline phosphatase					
ALP (isolated) > 2 × ULN if normal baseline or >2 x baseline if elevated before drug exposure (in the absence of known bone pathology)	
 • Repeat tests^a within 48 hours of notification of result 	↑	Both Parts 
 • Monitor LFT within 1 to 4 weeks or at next visit • Establish causality and complete liver event checklist (in SOM) 		-
Total bilirubin					
> 2 × ULN if normal baseline or >2 x baseline if elevated before drug exposure (in the absence of known Gilbert syndrome)	
 • Repeat tests^a within 48 hours of notification of result • Test for hemolysis (e.g., reticulocytes, haptoglobin, unconjugated [indirect] bilirubin) 	↑	Both Parts 
 • Discontinue study drug • Initiate close monitoring (evaluate 2-3 times a week with repeat tests^a) • Hospitalize if clinically appropriate • Establish causality and complete liver event checklist (in SOM) 		Both Parts 
 • Continue monitoring with Repeat tests^a until resolution^c
> 1.5 to ≤ 2 × ULN (patient is asymptomatic)	
 • Repeat tests^a within a week of notification of result 	↑	Both Parts If elevation from baseline is confirmed, initiate close observation of the patient i.e. evaluate 2-3 times a week with repeat tests ^a		Both Parts 
 • Repeat tests^a within 1 to 4 weeks or at next visit

Criteria	First Action	Result	Second Action	Result	Third Action
Jaundice	
 • Discontinue study drug • Initiate close monitoring (evaluate 2-3 times a week with repeat tests^a) • Hospitalize if clinically appropriate • Establish causality and complete liver event checklist (in SOM) 		Both Parts 
 • Continue monitoring with Repeat tests^a until resolution^c 		
Any AE potentially indicative of a liver toxicity*	
 • Consider study drug interruption or discontinuation • Hospitalization if clinically appropriate • Establish causality and complete liver event checklist (in SOM) 		Both Parts Investigator discretion		

*These events cover the following: hepatic failure, fibrosis and cirrhosis, and other liver damage-related conditions; the non-infectious hepatitis; the benign, malignant and unspecified liver neoplasms

^a Repeat tests: Physical examination and PT/INR and LFT: Liver function test: ALT, AST, GGT, alkaline phosphatase, total bilirubin, and albumin (see [Section 6.2.1](#));

^b(General) malaise, fatigue, abdominal pain, nausea, or vomiting, or rash with eosinophilia

^cResolution is defined as an outcome of one of the following: (1) return to baseline values, (2) stable values at three subsequent monitoring visits at least 2 weeks apart, (3) remain at elevated level after a maximum of 6 months, (4) liver transplantation, and (5) death.

Elevation confirmed or persisting, i.e. remain > 90% of the original elevated level

Decreasing elevation, i.e. decrease to ≤ 90 % of the original elevated level.

Table 15-2 Renal events: definition and follow up requirements

Renal Event	Actions
Serum creatinine $\geq 2 \times$ BL or ≥ 1.5 mg/dL	
1. Hold study medication
 
2. Confirm increase after 24-48h of notification of the value
 
3. If confirmed, permanently discontinue study medication
 
4. Follow up until resolution or stabilization of laboratory abnormality(ies)

Serum creatinine increase 25 – 49% compared to baseline during normal hydration status	
Confirm 25% increase after 24-48h of notification of the value
 
Follow up within 2-5 days

Serum creatinine increase $\geq 50\%$ compared to baseline	
Confirm $\geq 50\%$ within 24-48 hours after receipt of the abnormal value
 
If confirmation of abnormal value is not possible in this timeframe study drug must be withheld until further evaluation is possible
 
Consider drug interruption
 
Consider patient hospitalization / specialized treatment

Albumin- or Protein-creatinine ratio increase ≥ 2 -fold compared to baseline	Confirm value after 24-48h of notification of the value
Albumin-creatinine ratio (ACR) ≥ 30 mg/g or ≥ 3 mg/mmol;	Perform urine microscopy
New dipstick proteinuria $\geq 1+$	Consider drug interruption / discontinuation
Protein-creatinine ratio (PCR) $>$ ULN	
New dipstick glucosuria $\geq 1+$ not due to diabetes	
Blood glucose (fasting)
 
Perform serum creatinine, ACR

New dipstick hematuria not due to trauma	
Urine sediment microscopy
 
Perform serum creatinine, ACR

Document contributing factors: co-medication, other co-morbid conditions, and additional diagnostic procedures performed in the CRF	
Monitor patient regularly (frequency at investigator's discretion) until one of the following: Event resolution: (sCr within 10% of baseline or protein-creatinine ratio within 50% of baseline) Event stabilization: sCr level with $\pm 10\%$ variability over last 6 months or protein-creatinine ratio stabilization at a new level with $\pm 50\%$ variability over last 6 months.	

16 Appendix 2: Pruritus event definitions and required actions

The following table defines options for management of different CTCAE grades of pruritus. These include: concomitant medication administration; study drug interruption or withdrawal of study drug.

Table 16-1 Pruritus event definitions and required actions

Pruritus Event	Actions
CTCAE Grade 1 Mild or localized; topical intervention indicated	Treat with concomitant medication according to Investigator's discretion No option for drug interruption
CTCAE Grade 2 Intense or widespread; intermittent; skin changes from scratching (e.g., edema, papulation, excoriations, lichenification, oozing/crusts); oral intervention indicated; limiting instrumental ADL	Treat with concomitant medication according to Investigator's discretion No option for drug interruption
CTCAE Grade 3 Intense or widespread; constant; limiting self-care ADL or sleep; oral corticosteroid or immunosuppressive therapy indicated	Treat with concomitant medication according to Investigator's discretion Option for drug interruption of up to 1 week

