6.2.1 Permitted dose adjustments and interruptions of study treatment

Part 1

Within a cohort, once a dose is decided on, study drug dose adjustments are not permitted.
Interruption to study drug may occur based on the criteria outlined in [Table 15-1](#) (Liver events)
and [Table 6-1](#) (Pruritus event definitions and required actions).

In case of notable adverse events or safety concerns during dose escalation of the study, the following changes to the next planned dose level may be considered:

- Administration of a dose below the starting dose
- Administration of an intermediate dose between the current and preceding dose
- Administration of an intermediate dose between the current and next planned dose
- Repeated administration of the current dose
- Termination of any further dose escalation

These changes must be recorded on the Dosage Administration Record CRF.

Part 2: Option for dose reduction when ALT or AST > 2 x Baseline value AND $\leq 8 \times \text{ULN}$

For patients who experience ALT or AST elevations meeting the definitions outlined in [Table 15-1](#), a dose interruption or dose reduction to the next lower dose level, (or to placebo if receiving the lowest dose level) is permitted. One dose reduction step is allowed per patient. If, despite being on a reduced dose, a patient has persistent (i.e. remains $> 90\%$ of the original elevated level) or new ALT or AST elevation, they must be discontinued from study treatment. Increasing the dose to the original level is not permitted.

If the patient has symptoms or other LFTs are also elevated please refer to [Appendix 1](#) for appropriate actions.

Patients with AST or ALT values meeting the requirement will be instructed to return to the clinic for an additional visit, where repeat tests will be performed, including a physical examination and laboratory assessment including ALT, AST, GGT, alkaline phosphatase, total bilirubin, albumin and PT/INR.

The central laboratory should be used, if this is not possible, the repeats can be performed at a local laboratory to monitor the safety of the patient. If tests are performed at local laboratory, results will be captured in source documents only. In all cases, a physical examination should be performed and recorded in source documents.

Table 15-1 in [Appendix 1](#) outlines the required testing frequency and resultant actions dependent on the outcome of the repeat assessments.

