8.4.4 Laboratory evaluations

Clinically relevant deviations of laboratory test results occurring during or at completion of the study must be reported and discussed with Novartis personnel. The results should be evaluated for criteria defining an adverse event and reported as such if the criteria are met. Repeated evaluations are mandatory until normalization of the result(s) or until the change is no longer clinically relevant. In case of doubt, Novartis personnel should again be contacted.

Hematology

Hemoglobin, hematocrit, red blood cell count, white blood cell count with differential and platelet count will be measured.

Clinical chemistry, including fasted lipid panel

Sodium, potassium, bicarbonate, creatinine, urea, uric acid, chloride, calcium, alkaline phosphatase, total bilirubin, LDH, GGT, AST, ALT, albumin, aPTT, PT/INR, CK, glucose, total cholesterol, HDL, LDL, triglycerides, magnesium, phosphate and vitamin D. If the total bilirubin concentration is increased above 1.5 times the upper limit of normal, direct and indirect reacting bilirubin should be differentiated.

Urinalysis

Urine test by dipstick e.g., Combur9: leucocytes, nitrite, pH, protein, glucose, ketones, urobilinogen, bilirubin, blood/ hemoglobin.

If the dipstick result is positive for protein, nitrite, leucocytes and/or blood, the sample will be sent for microscopic analysis of WBC, RBC and casts.

Special clinical laboratory evaluations

- Alpha-fetoprotein (performed only at screening)
- Blood type (performed only at screening)

Detailed information on special clinical laboratory assessments will be provided in the laboratory manual and the SOM.

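### Table 15-1 has no ALT/AST row for a symptomatic patient above 2 x baseline but at or below 3 x ULN, although the same value without symptoms triggers mandatory action

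*Protocol*

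**What the plan says.** Table 15-1 (Protocol, Appendix 1) has six ALT/AST rows. Two matter most here.

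- The symptomatic row, "ALT or AST > 2 X Baseline AND > 3 x ULN AND accompanied by symptoms", requires study drug to be discontinued at once. Footnote b defines symptoms as (general) "malaise, fatigue, abdominal pain, nausea, or vomiting, or rash with eosinophilia".
- The low-elevation row, "ALT or AST > 2 X Baseline AND ≤ 5 × ULN (patient is asymptomatic"), requires repeat tests within 48 hours of notification. The table's key defines a positive repeat as "Elevation confirmed or persisting, i.e. remain > 90% of the original elevated level". If the repeat is positive, Part 1 discontinues study drug. Part 2 holds it, repeats within another 48 hours, and reduces the dose if the value is still elevated.

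Section 6.2.1 offers Part 2 dose reduction for ALT or AST above 2 x baseline and up to 8 x ULN, for elevations that meet the Table 15-1 definitions. It then adds: "If the patient has symptoms or other LFTs are also elevated please refer to" Appendix 1.

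Three other provisions bear on the point:

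- The last row of Table 15-1, for any AE that may indicate liver toxicity, opens with "Consider study drug interruption or discontinuation".
- Section 8.4.4 says of clinically relevant laboratory deviations: "Repeated evaluations are mandatory until normalization of the result(s) or until the change is no longer clinically relevant".
- Section 7.1 lists the general reasons for stopping treatment.

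**The concern.** Between 3 and 5 x ULN the table escalates as one would expect: symptoms move a patient from repeat testing to immediate discontinuation. At or below 3 x ULN the direction reverses. Symptoms take the patient out of the only row that applies and put nothing in its place, so the more worrying presentation has the less defined response.

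The restriction to asymptomatic patients was probably meant to send symptomatic patients to the stricter row. That row starts only above 3 x ULN, so the two do not meet.

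What is at stake is patient safety and consistency between sites. Section 9.3 calls for a standardized process for liver events. Section 3.6 reports isolated transaminase increases in an earlier study of this drug, and Section 7.1 anticipates nausea and vomiting. Symptoms together with a transaminase rise are therefore foreseeable.

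**Working it through.** No sample size, power or error rate is involved. The check is whether the rows cover every case. Write b for baseline and x for the on-treatment value, both in multiples of ULN.

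**Step 1: the six ALT/AST rows.**

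| Row | Condition on ALT or AST | Open to a symptomatic patient? |
|---|---|---|
| Potential Hy's Law | x > 3, with bilirubin and ALP conditions | Yes |
| Raised INR | x > 3, with INR > 1.5 | Yes |
| High | x > 8 | Yes |
| Symptomatic | x > 2b and x > 3 | Yes (symptomatic only) |
| Middle | x > 2b and 5 < x ≤ 8 | Yes |
| Low | x > 2b and x ≤ 5 | **No** |

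Every row marked Yes needs x > 3. Bilirubin or INR cannot rescue a case at x ≤ 3 through an ALT/AST row, because those two rows also need x > 3.

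**Step 2: the uncovered region.** A symptomatic patient meets no ALT/AST row when 2b < x ≤ 3. That interval is non-empty only if 2b < 3, that is, b < 1.5.

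The four rows that do not depend on bilirubin or INR were evaluated on a grid of b from 0.2 to 5.0 and x from 0.1 to 12.0 in steps of 0.1, keeping points with x > 2b:

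- Without symptoms: 0 uncovered points.
- With symptoms: 182 uncovered points, all with b between 0.2 and 1.4 and x no higher than 3.0.

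**Step 3: can a trial patient be there?** Yes. Section 4.1 caps ALT/AST at 5 x ULN and sets no lower limit. Disease severity at entry is defined by ALP or bilirubin. Baselines below 1.5 x ULN are therefore eligible in both parts.

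**Step 4: width of the gap.** The gap is (2b, 3] and the low row spans (2b, 5], so the share of that row's range is (3 − 2b)/(5 − 2b).

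| Baseline b | Gap (x ULN) | Share of the low row's range |
|---|---|---|
| 0.8 | 1.6 to 3.0 | 1.4/3.4 = 41% |
| 1.0 | 2.0 to 3.0 | 1.0/3.0 = 33% |
| 1.2 | 2.4 to 3.0 | 0.6/2.6 = 23% |
| 1.4 | 2.8 to 3.0 | 0.2/2.2 = 9% |
| 1.5 | none | 0% |

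These are shares of a numerical range at illustrative baselines, not shares of patients.

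**Step 5: one patient, two presentations.** Take baseline 1.0 and on-treatment value 2.6.

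- Without symptoms: repeat within 48 hours. The elevation is confirmed if the repeat exceeds 0.9 × 2.6 = 2.34. The Part 1 or Part 2 drug action follows.
- With nausea or fatigue: no ALT/AST row applies.
- With the same symptoms at 3.2: the symptomatic row applies and study drug is discontinued.

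**The case against.** The literal gap is hard to dispute. The case on the other side is that it matters little.

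- **Section 6.2.1 may cover Part 2.** Its heading carries no symptom limit, and it describes a return visit, repeat tests and a blinded dose reduction. The referral to Appendix 1 could mean only that the site should check for a stricter row. That reading is possible, so Part 2 is ambiguous rather than plainly empty. But the section ties its action to the Table 15-1 definitions and sends symptomatic patients to a table with no matching ALT/AST row. It offers nothing for Part 1.
- **The liver-toxicity AE row may apply.** It also asks for a causality assessment and the liver event checklist, and its footnote extends to other conditions related to liver damage. This stands in part. Whether doubled transaminases with fatigue qualify is a judgement, the footnote b symptoms are not listed there, and the drug action is only to be considered.
- **Some general rules are mandatory.** Section 7.1 requires stopping for GI symptoms deemed intolerable, and Section 8.4.4 requires repeats of clinically relevant deviations and discussion with the sponsor. It is fair to say that a patient left unmonitored is unlikely. None of these rules sets a 48-hour repeat or a hold pending the result.
- **The low row has no floor in ULN.** With a baseline of 0.4 x ULN, a normal value of 0.85 x ULN exceeds 2 x baseline (0.8). Opening the row to symptomatic patients could make a Part 1 patient with fatigue and a confirmed normal ALT stop treatment. This is a real cost. It is also a feature the row already has for asymptomatic patients.

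**Conclusion.** The concern holds. A patient with footnote b symptoms, a baseline below 1.5 x ULN, and ALT or AST above 2 x baseline but no higher than 3 x ULN meets no ALT/AST row of Table 15-1, while the same value without symptoms triggers defined steps. This assumes that the table is read as written and that the other enzyme does not itself meet a row. The gap is clearest in Part 1, where the asymptomatic patient with a confirmed elevation is taken off drug and no other text supplies an equivalent step. In Part 2 the text is at best ambiguous.

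The band is narrow, and other safeguards make serious neglect unlikely. The number of patients affected depends on the baseline ALT/AST distribution, which the documents do not give. It should still be corrected, because the table reverses its own escalation logic in a safety rule.

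**What to change.** In the low-elevation row of Table 15-1, replace the restriction to asymptomatic patients with wording such as *and not meeting the symptomatic > 3 x ULN row*. Symptomatic patients at or below 3 x ULN then receive at least the same repeat testing, hold and dose action. Immediate discontinuation above 3 x ULN with symptoms keeps precedence, and the Section 6.2.1 referral then leads to a row that applies.

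The cost is one phrase in one row, made by protocol amendment. No numerical threshold changes, and nothing changes for asymptomatic patients. Symptomatic patients in the band have extra liver tests, and some will stop or reduce study drug, including a few whose values are still within the normal range because the row has no floor. If the sponsor finds that last consequence unwelcome, a floor in ULN could be considered for all patients, but that is a separate decision.
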